All cases will be managed according to the sponsor's Pharmacovigilance processes, in line with the applicable legislation.

Whenever applicable, individual case safety reports (ICSRs) will be submitted to Health Authorities on an expedited basis according to current regulations.

Progress status updates will be given in each Periodic Safety Update Report (PSUR) and Development Safety Update Report (DSUR) if applicable.

Additionally, a descriptive analysis of the data collected will be provided annually in the PSUR.

Study duration and dates

Recruitment of women will be done using a website access. Implementation of the website is planned for the second quarter of 2014 and website will be in place during the whole course of the study.

STUDY SCHEDULE

Period of pregnancy Study procedures	Enrolment in the study	Pregnancy Course	End of pregnancy	4 months FU ³
Written ¹ informed consent	X			
Inclusion criteria	X			
Pregnancy diagnosis	X			
ella [®] exposure	X			
Prior and concomitant medications	X	X	X	
Recreational drug use (tobacco, alcohol, illicit drugs)	X	X	X	
Serology and prenatal tests results	X			
Medical history	X			
Maternal and fetal pregnancy complication	X	X	X	
Pregnancy outcome ²			X	
Live birth follow-up ³				X

¹: Signed ICF will be collected according to local regulations. When completed by the HCP, prior starting the questionnaire completion, the ICF will be downloaded from the website and a print-out copy signed by the woman. When completed by the woman, prior starting the questionnaire completion, an electronic signature will be requested on the ICF module and the woman will be requested to save and/or print the ICF for her records.

²: Possible pregnancy outcomes are: Live birth (healthy baby, congenital anomaly or other neonatal diagnosis, or neonatal death); pregnancy loss (spontaneous abortion or ectopic pregnancy or induced abortion, premature stillbirth)

³: In case of live birth, the period of observation of the study will last for 4 months post-delivery to access possible congenital anomalies that may not be detected at birth.

ABBREVIATIONS AND DEFINITIONS

ADR	Adverse Drug Reaction
AE	Adverse Event
AFP	Alpha-Fetoprotein
CFR	Code of Federal Regulations
CHMP	Committee for Medicinal Products for Human Use
CRO	Contract Research Organization
DMB	Data Monitoring Board
DSUR	Development Safety Update Report
EC	Emergency Contraception
EUROCAT	European Surveillance of Congenital Anomalies

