8.2.1.4 Completion of the 4-month Follow-Up HCP Forms

In case of live birth and 4 months after the delivery, the HCP be reminded to re-access the website. The HCP will be asked to:

- Access the website with the HCP unique user ID and password
- Collect the age, height and weight of the baby
- Collect congenital anomaly detected since birth, if applicable
- Collect late development detected since birth, if applicable
- Collect death data, if applicable.

8.2.2 Completion of the on-line questionnaire directly by the woman:

Up to three questionnaires will be completed by the woman: the first two ones including Pregnancy and Outcome Forms, and one for live birth only, a 4-month Follow-up Form.

* In case a woman completed the questionnaire on her own, she should be reminded to bring her unique patient number to allow the HCP to provide further information on the pregnancy if requested.

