8.4 Methods of data collection

Online questionnaires for data collection will be available on a dedicated and secured website. Once submitted, these questionnaires will be received by the Sponsor's drug safety department.

Specific questionnaires may be completed on-line either by the HCP or directly by the woman at any time from pregnancy diagnosis up to known pregnancy outcome.

There will be a specific on-line questionnaire to be completed by the HCP where data on pregnancy diagnosis and exposure to ella® will first be collected. Once the pregnancy outcome is known, the HCP will be requested to complete the rest of the questionnaire.

For live birth only (except for neonatal death), HCP will be requested to complete a follow-up questionnaire 4 months after the delivery date (**4 month Follow-Up HCP Form**).

When completed directly by the woman, the woman will have to complete a simplified questionnaire where data on pregnancy diagnosis, exposure to ella®, and if known at the time of the questionnaire completion, the pregnancy outcome.

For live birth only (except for neonatal death), the woman will be encouraged to fill in a 4-month Follow-Up Form around 4 months after the delivery date (**4 month Follow-Up Woman Form**).

The on-line questionnaires together with instructions will be available in English for the HCP and in both English and Spanish for the woman.

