9.2 Statistical analyses

9.2.1 Study Population

The data collected in this study will be pooled with all reports of pregnancies collected by the Sponsor which include information on pregnancy outcome. Additional data sources include other past and current clinical trials and spontaneous pharmacovigilance reporting. Pregnancy outcomes will be analyzed on the pooled dataset.

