9.2.2.2 Primary Objective Assessments

The primary objective of this observational study is to estimate the rates of occurrence of outcomes of pregnancies exposed to ella® in order to detect a possible signal of concern for adverse outcomes related to exposure to ella®.

Each pregnancy outcome will be described by proportions (cumulative incidence/prevalence) with exact 95% confidence interval.

For each pregnancy outcome, data from all sources (past and current clinical trials, registry, spontaneous pharmacovigilance reporting) will be used. Outcomes to be evaluated are defined as follows:

All Induced abortions (due to a medical/non-medical reason):

Proportion of normal-appearing pregnancies (with analysable ultrasound results) before induced abortion = number of normal-appearing pregnancies with ultrasound compatible with normal growth and development/ number of pregnancies with analysable ultrasound results.

Therapeutic abortion (medical indication)

Proportion of therapeutic abortions = number of therapeutic abortions / number of pregnancies

Birth outcomes

Proportion of live births = number of live births/ total number of births

Proportion of healthy babies = number of live births without any anomaly (healthy babies) / number of deliveries

Total live birth prevalence of congenital anomalies = number of live births with congenital anomalies / number of live births

Proportion of neonatal deaths = number of neonatal deaths / number of live births

Congenital anomalies:

Total prevalence of congenital anomalies = total number of congenital anomalies (terminations of pregnancy for fetal anomaly (TOPFA), stillbirths, live births with congenital anomalies / total number of births (live births + stillbirths)

Pregnancy loss outcomes

Proportion of spontaneous abortions (or spontaneous abortion cumulative incidence) = number of spontaneous abortions / number of pregnancies

Proportion of intermediate fetal deaths* = number of intermediate fetal deaths / number of pregnancies

Proportion of stillbirths (or stillbirth cumulative incidence) = number of stillbirths / number of pregnancies

* more than 20 completed weeks of gestation but less than 28, according to the WHO fetal death classification.

Proportion of ectopic pregnancies (or ectopic pregnancy cumulative incidence) = number of ectopic pregnancies / number of pregnancies with known outcomes reported

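### Congenital anomaly prevalence divides anomalies found at any time by all pooled live births, although only infants with 4-month or equivalent follow-up are systematically assessed for anomalies not detected at birth

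*Protocol*

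**What the plan says.** - **The rule.** Protocol section 9.2.2.2 gives "Total live birth prevalence of congenital anomalies = number of live births with congenital anomalies / number of live births". For every outcome in that section, "data from all sources (past and current clinical trials, registry, spontaneous pharmacovigilance reporting) will be used". Total prevalence (over live births plus stillbirths) and the healthy-baby proportion (over deliveries) draw on the same anomaly counts among live births.
- **Entry to the pool.** Section 9.2.1: "The data collected in this study will be pooled with all reports of pregnancies collected by the Sponsor which include information on pregnancy outcome". It adds: "Additional data sources include other past and current clinical trials and spontaneous pharmacovigilance reporting". Infant follow-up is not a condition of entry.
- **Purpose of the 4-month step.** Study Schedule, footnote 3, on liveborn infants: "the period of observation of the study will last for 4 months post-delivery to access possible congenital anomalies that may not be detected at birth". The health care professional's (HCP's) form in section 8.2.1.4 has the item "Collect congenital anomaly detected since birth, if applicable", and section 8.2.2.3 has a matching item for the woman.
- **Strength of the request.** Section 8.4 says "the woman will be encouraged to fill in a 4-month Follow-Up Form around 4 months after the delivery date". Other places are firmer. Sections 4.2.1 and 4.2.2 request the form, 8.2.1.4 provides a reminder to the HCP, 8.2.2.3 an e-mail to the woman, and 14.1 a contact at 4 months. The two repeat contacts in section 8.3 concern the HCP and the delivery outcome; none is stated for the 4-month step.
- **Incomplete follow-up.** Section 9.2.2.1 has the proportion lost to follow-up described. No rule ties it to the anomaly denominators.

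**The concern.** The design treats detection at birth as incomplete, and the prevalence rule does not reflect that. The numerator accepts an anomaly whenever it was found. The denominator counts every live birth, whether or not anyone looked at the infant again. An infant last reported on at delivery therefore counts as unaffected at 4 months without having been assessed.

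Elsewhere section 9.2.2.2 limits denominators to what could be assessed: the ultrasound proportion uses only pregnancies with an analysable scan, and the ectopic proportion only those with a known outcome. The anomaly prevalence has no such limit.

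The stated aim of the section is to detect a possible signal, and the synopsis plans a comparison with registry data such as EUROCAT. A figure that blends two detection windows in unknown proportion, differing by data source, is hard to set against any single reference figure.

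**Working it through.** **Plan's own figure.** Annex 1, Table 1 gives 398 exposed pregnancies for 3% against 6%, and 392 for 1% against 3% (two-sided alpha 0.05, 80% power, 1:10). With k = 10, d the difference in proportions, p₁ the exposed and p₂ the unexposed proportion, and p̄ = (p₁ + 10p₂)/11:

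n = [1.96·√(p̄(1 − p̄)·1.1) + 0.842·√(p₁(1 − p₁) + p₂(1 − p₂)/10)]² / d²

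This gives 362 and 339. The continuity correction, n/4 × [1 + √(1 + 2.2/(n·d))]², brings them to 398 and 392. Table 1 is reproduced and is not in dispute.

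**Effect of the denominator.** Let s be the share of live-birth anomalies first detected after birth, and c the share of live births with 4-month data. If return of the form is unrelated to anomaly status and no other route adds late findings:

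observed/true = (1 − s) + s·c = 1 − s(1 − c)

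The protocol gives neither s nor c. Both are assumptions here:

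| s | c = 90% | c = 75% | c = 50% | c = 25% |
|---|---|---|---|---|
| 10% | 0.990 | 0.975 | 0.950 | 0.925 |
| 30% | 0.970 | 0.925 | 0.850 | 0.775 |
| 50% | 0.950 | 0.875 | 0.750 | 0.625 |

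**In risk ratios.** Against a fully ascertained reference, a true risk ratio of 2 would appear as 2 × 0.99 = 1.98 at one end and 2 × 0.625 = 1.25 at the other. At s = 30% and c = 50% it would appear as 2 × 0.85 = 1.70. Power with 400 exposed would then fall from 80% to about 56% (3% baseline, risk ratio 2), and from 81% to about 66% (1% baseline, risk ratio 3). This takes all 400 as live births, whereas the protocol's 400 are pregnancies with known outcome.

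**In events.** At twice the Table 2 live birth prevalence (2 × 1.76% = 3.52%), 400 live births yield 14.08 affected infants. The shortfall runs from 14.08 × 0.01 = 0.14 to 14.08 × 0.375 = 5.28 infants.

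**Selective return.** Take a true prevalence of 3% and s = 30%, so 2.1% are known at birth and 0.9% found later. Suppose 80% of affected and 50% of other families return the form.

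- Protocol rule: 2.1% + 0.9% × 0.8 = 2.82%.
- Completers only: 3% × 0.8 / (3% × 0.8 + 97% × 0.5) = 2.4/50.9 = 4.7%.
- Two-window estimate p_birth + (1 − p_birth) × p_new: p_new = 0.72/(0.72 + 48.5) = 1.46%, so 2.1% + 0.979 × 1.46% = 3.5%.

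If 50% return in both groups, the protocol rule gives 2.1% + 0.45% = 2.55%. The two-window estimate has p_new = 0.45/(0.45 + 48.5) = 0.92% and gives 2.1% + 0.979 × 0.92% = 3.0%.

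**The case against.** A reader might infer that only infants with a completed 4-month form can contribute late-detected anomalies, and that the prevalence is therefore biased downward. The documents do not support either step.

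- **Other routes exist.** The woman can reopen her file at any time (section 8.2.2.2), the sponsor can query reporters about the baby (8.3), and anomalies can arrive as individual case safety reports (10). These can raise the share of late anomalies captured above c. They do not amount to a systematic assessment of every infant.
- **The net direction is open.** Voluntary and spontaneous reporting, and entry as late as the known outcome, may over-represent affected infants and push prevalence up.
- **The reference window is missing.** Table 2 does not state how long after birth the registry detects anomalies. The risk ratios above hold only for a fully ascertained reference.
- **The size is assumed.** At s = 10% and c = 90% the loss is 1%, which is negligible.
- **Any correction has its own bias.** Under selective return the two-window estimate (3.5%) lies further from 3% than the protocol rule (2.8%).

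All of this stands, and it limits the claim. It can also be said that section 9.2.2 leaves planned analyses to the statistical analysis plan, which is not available here, and that loss to follow-up will be described. That part is weaker. Section 9.2.2.2 itself fixes the numerator, the denominator and the pooled sources, so the point concerns a stated rule and not an omitted detail.

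**Conclusion.** The concern holds in a limited form. As written, the rule mixes two detection windows and counts infants never assessed after birth as free of late-detected anomalies. This mechanism alone pulls down the live birth prevalence and the live-birth part of total prevalence, and pushes the healthy-baby proportion up. Fetal anomalies in terminations and stillbirths are not affected by it.

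The ratio of observed to true prevalence lies between about 0.99 and 0.625 over the assumed values. That range presumes form return unrelated to anomaly status and no late findings by other routes. It runs from negligible to large, and the documents do not allow it to be narrowed. They do not establish a net downward bias, or that the comparison with the registry is pushed towards no increase. Nor does section 9.2.2.2 single out anomaly prevalence as the main safety measure. The definition should be changed because, as it stands, the reported figure cannot be interpreted without knowing how many infants were followed.

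**What to change.** In section 9.2.2.2, keep the all-live-births figure and split it by detection window:

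- (a) anomalies known at the birth or outcome report, over all live births (over all births for total prevalence);
- (b) anomalies newly detected after birth, over infants with no anomaly at birth and with completed 4-month or equivalent follow-up.

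Give the combined 4-month prevalence, p_birth + (1 − p_birth) × p_new, as a companion estimate beside the all-live-births figure, not as its replacement. State that it assumes return of the form is unrelated to anomaly status and can err upward if affected families return more often. Do not present an infant without 4-month data as anomaly-free at 4 months. Report the share of live births with 4-month data by source, and compare each window with a reference figure of the same detection window where one is available.

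The cost is revised wording and a flag per infant for follow-up and time of detection. The 4-month component rests on fewer infants and has a wider interval, and selective return remains a risk. Past trials and spontaneous reports may not record when an anomaly was detected; those cases should be shown as unknown.

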4 SELECTION OF WOMEN

4.1 Number of women

As per rationale detailed in section 9.1, a total of 400 ella®-exposed pregnancies with known outcomes will be analysed.

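### The spontaneous abortion cumulative incidence is spontaneous abortions over all pooled pregnancies, whenever first reported, so it depends partly on when and why pregnancies are reported

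*Protocol*

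**What the plan says.** Section 9.2.2.2 lists the outcome definitions for the primary objective. For miscarriage it gives "Proportion of spontaneous abortions (or spontaneous abortion cumulative incidence) = number of spontaneous abortions / number of pregnancies". Section 8.1 counts losses before 20 completed weeks as spontaneous abortion.

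The analysis set is this study's data "pooled with all reports of pregnancies collected by the Sponsor which include information on pregnancy outcome" (section 9.2.1), and section 9.2.2.2 names past and current trials, the registry and spontaneous pharmacovigilance reports as sources for each outcome. Section 4.1 says that 400 exposed "pregnancies with known outcomes will be analysed".

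On entry, sections 3 and 8.4 let a questionnaire be completed "at any time from pregnancy diagnosis up to known pregnancy outcome". Section 4.2.2 lets a woman give an outcome already known when she first fills in the form, and section 14.1 foresees professionals reporting once an outcome is known. The only planned breakdowns of the proportions are by country and age. Gestational age at first report is not among the baseline items in section 9.2.2.1.

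Section 9.2.2.4 would test event proportions against a reference group if an appropriate one exists. Section 9.1 uses miscarriage as its example of an event at 20%, and counts a 50% increase from 20% as detectable with about 160 exposed pregnancies.

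**The concern.** A cumulative incidence needs a group followed from a common starting point, and this design has none. A woman who first reports a continuing pregnancy at week 15 has already passed much of the window in which a spontaneous abortion can occur, yet she counts fully in the denominator. Comparable pregnancies lost before they would have been reported may never appear. Conversely, a report prompted by a loss adds to the numerator however many comparable continuing pregnancies go unreported.

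The two mechanisms pull in opposite directions, and nothing in the protocol separates or corrects them. The professional contacts at 20 weeks and at delivery (sections 8.3 and 14.1) reduce loss to follow-up after entry but do not change when a pregnancy enters. At stake is a primary outcome meant to reveal a safety signal: a real increase could be diluted, or an unchanged risk could look raised.

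**Working it through.** **The plan's own figures.** The two-proportion formula with two-sided alpha 0.05, 80% power, 1:10 allocation and continuity correction returns Table 1 (Annex 1): 164 exposed for 20% against 30%, and 46 for 20% against 40%. The planning arithmetic is not at fault.

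**Inputs from the protocol.** Reference 20%; 400 known outcomes; 1:10, hence 4,000 reference pregnancies; risk window up to 20 weeks.

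**Assumptions not in the protocol.**
- Loss hazard over weeks 4-20 falling at rate k = 0.25 or 0.10 per week, or constant (k = 0).
- First report planned uniformly over weeks 4-12 or 4-20.
- No induced abortion.
- A share r of pregnancies that ended before the planned report is still reported.

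**Share of losses before the planned report.** With true risk p, f = (1/p) × average over the entry window of [1 − (1−p)^C(t)], where C(t) = (1 − e^(−k(t−4))) / (1 − e^(−16k)), or (t−4)/16 when k = 0.

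**Downward case.** Observed proportion = p[1 − (1−r)f] / [1 − (1−r)pf].

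Example: p = 0.30, f = 0.611, r = 0.5 gives 0.30 × 0.6945 / (1 − 0.0917) = 0.2084/0.9083 = 0.229.

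Power (pooled variance, no continuity correction): pooled proportion (400 × 0.2294 + 800)/4,400 = 0.2027; null SE 0.0211; alternative SE 0.0220; z = (0.0294 − 1.96 × 0.0211)/0.0220 = −0.54; power 29%.

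True 30%, shown as observed proportion (power):

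| k | Entry weeks | f | r = 0.5 | r = 0.75 | r = 0.9 |
|---|---|---|---|---|---|
| 0.25 | 4-12 | 0.611 | 22.9% (29%) | 26.6% (86%) | 28.7% (97%) |
| 0.10 | 4-12 | 0.426 | 25.2% (68%) | 27.7% (94%) | 29.1% (98%) |
| 0 | 4-12 | 0.280 | 26.9% (88%) | 28.5% (97%) | 29.4% (99%) |
| 0.25 | 4-20 | 0.788 | 20.6% (5%) | 25.6% (74%) | 28.3% (96%) |
| 0.10 | 4-20 | 0.655 | 22.4% (21%) | 26.4% (83%) | 28.6% (97%) |
| 0 | 4-20 | 0.530 | 24.0% (47%) | 27.1% (90%) | 28.9% (98%) |

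At r = 1 the observed value is 30% with 99% power: no bias. At r = 0.5 with entry over weeks 4-8, a true 30% shows as 25-28%. A true 40% at r = 0.5 shows as 29-36% over the six settings in the table, with power of at least 97%.

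**Upward case.** All ended pregnancies are reported, continuing ones a fraction c as often: observed = [pf + cp(1−f)] / [pf + c(1−pf)].

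Example: p = 0.20, f = 0.599 (k = 0.25, weeks 4-12), c = 0.5 gives (0.1198 + 0.0401)/(0.1198 + 0.4401) = 0.1599/0.5599, about 0.286.

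Over the six settings a true 20% shows as 24-31%, and the chance of a significant excess runs from about 49% to over 99%. With c = 0.8 it shows as 21-23%, and the chance is 8-30%.

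**Crude proportion in the prospective subset.** This is r = 0: p(1−f)/(1−pf). A true 40% then shows as 12-36% over all hazards and entry windows (weeks 4-8 included), lower than the pooled figure in the same setting. Restricting to prospective reports without a delayed-entry estimate makes the downward bias worse.

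**The case against.** The size rests on assumptions. With 90% of ended pregnancies reported, power for a 50% increase stays at 96-99%. The lowest powers need only half of them reported and entry spread to week 12 or 20. One entry pattern is also applied to sources as different as trials and spontaneous reports. The 400 was chosen for a doubling at 3% and a tripling at 1%, not for miscarriage. Section 9.2.2 defers planned analyses to an SAP not at hand, and testing is conditional on an appropriate reference. Each of these limits the weight of the point. None removes it, because section 9.2.2.2 itself fixes the formula and the label.

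A reader might infer three stronger things that the protocol does not support.

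- That pregnancies of unknown outcome dilute the proportion. The ectopic formula does specify "number of ectopic pregnancies / number of pregnancies with known outcomes reported" and the miscarriage formula does not, but sections 4.1 and 9.2.1 already limit the analysis to known outcomes.
- That "Proportion of intermediate fetal deaths* = number of intermediate fetal deaths / number of pregnancies" and "Proportion of stillbirths (or stillbirth cumulative incidence) = number of stillbirths / number of pregnancies" are equally faulty. Deaths per pregnancy is a legitimate measure. Its denominator misleads only against a per-birth reference, and none is specified.
- That a doubling would be missed. Without induced abortion it is not. If half the women intend induced abortion near week 8, a true 40% shows as 24-28% (power about 44-94%). But full reporting would itself give 26-33%, so much of that drop comes from a reference that does not match on induced abortion, not from reporting time.

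**Conclusion.** The point holds for spontaneous abortion only. The stated definition mixes pregnancies that entered at different gestational ages with pregnancies reported after they had ended, and calls the result a cumulative incidence. It can be biased either way, and the protocol gives no entry-time, retrospective-report or induced-abortion shares from which to say which way or how far.

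Under the assumed patterns the distortion runs from none (complete reporting) to a 50% increase nearly vanishing, or an unchanged risk showing as about 1.2 to 1.5 times the reference (24-31% against 20%). This is worth correcting because the outcome serves signal detection and the remedy uses data that the forms largely collect. Confidence is medium: the mechanism follows from the text, the magnitude does not.

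**What to change.** - Keep the crude proportion as description, shown separately for pregnancies first reported before and after the outcome was known.
- Base any comparison under section 9.2.2.4 on pregnancies reported before 20 weeks with outcome unknown. Use a delayed-entry cumulative incidence by gestational age: entry at gestational age at first report, induced abortion as a competing event.
- Start the estimate at a week with a prespecified minimum number at risk. Compare it with a reference risk from that same week that treats induced abortion the same way. If no such reference is found, report the comparison as descriptive only.
- Do not compare the crude proportion of the prospective subset with the reference.
- Leave the stillbirth and intermediate fetal death formulas as they are, but require any reference rate to use the same denominator.

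**Cost.** LMP and gestational age at loss are collected (section 8.1), and the online submission supplies the report date; entry dates may be missing in some pooled sources. Under the assumptions above with r = 0.5, about 324-375 of 400 reports stay in the comparison, or 246-323 if half intend induced abortion. In simulation without induced abortion, the standard error from week 5 is about 3-5 points (5-9 from week 4) against about 2 for the crude proportion. Power for a doubling is then 89% to nearly 100%. For a 50% increase it is 68% / 39%, 83% / 63% and 89% / 75% (entry to week 12 / 20, for k = 0.25, 0.10 and 0), against 29% / 5%, 68% / 21% and 88% / 47% crude. The quantity also changes: at k = 0.25 a true 20% by week 20 becomes a target of 15.9% from week 5, which is why the reference must start at the same week.
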